1.0 BACKGROUND AND RATIONALE

1.1 Study Synopsis

In this feasibility study, up to 140 patients undergoing elective thoracic surgery will be randomized to one of two arms to complete PRO (patient reported outcome) symptom monitoring. The two arms are 1) active symptom monitoring and 2) passive symptom monitoring. The participants randomized to active symptom monitoring will have alerts sent to their clinicians when their PRO symptom scores exceed baseline discharge day scores (when discharge day scores are available) by 2 points or more, or when 'severe' or 'very severe' symptoms are reported. Participants randomized to the passive PRO monitoring arm will complete the same PROs as participants in the active monitoring arm, but will not have alerts sent to their clinician.

The overall goal of this study is to assess whether collecting and monitoring patient-reported data is feasible as part of clinical care of thoracic surgery patients, and whether these data are useful for clinicians and patients. Among these 140 patients, a subset of approximately 40 patients and their 40 caregivers will be chosen to complete a semi-structured interview, if willing, to assess patient experience with monitoring experience.

1.2 Background

Patient-centered outcomes after surgery go beyond traditionally measured morbidity and mortality to include QOL [11]. Patients undergoing thoracic surgery strongly value communication from their providers about anticipated physical functioning post-operatively [12, 13]. Patients who require thoracic surgery are older, have comorbidities, and have greater decreases in QOL after often morbid treatments compared to other patients [14]. Therefore, 90-day readmissions after thoracic surgery remain high at 18%, largely due to symptomatic adverse events including post-operative complications and new cardiopulmonary diagnoses [4, 15]. While symptom severity and physical functioning worsen for up to 6 months after thoracic surgery [16-18], pain and QOL do return to baseline by 12 months [19], suggesting a window in the first year after surgery during which PROs can be better monitored and managed.

In non-surgical populations, management of patient-reported symptoms has been extensively linked to improvements in care delivery including readmissions. The NIH has developed a PRO version of the Common Terminology Criteria for Adverse Events (PRO-CTCAE), which is a validated library assessing the presence, frequency, severity, and interference with usual activities of symptoms. Responses are provided by patients on a 5-point Likert scale with recall being over the prior week [20]. PRO-CTCAE is feasible for use in a variety of patient populations [21]. In surgical patients, PROs have been used as clinical outcomes, for quality improvement, and as outcomes in comparative effectiveness research [22]. In thoracic surgery patients specifically, PRO assessment through weekly

telephone surveys has demonstrated symptom improvement; however, items assessed were standard cancer-related and one surgical specific symptom. Further, only 60% of symptom alerts lead to intervention by clinicians [8].

Currently, PROs including symptoms and QOL are not routinely collected in thoracic surgery patients. Challenges include selecting a comprehensive, sensitive instrument, time and knowledge required to administer and analyze responses, and integration into existing systems for outcomes measurement [9]. Nonetheless, a pilot study integrated empirically selected symptom items from PROMIS with the Society of Thoracic Surgeons (STS) National Database [16]. The potential value of using PROs in perioperative care is multifaceted and includes shared-decision making, increasing patient satisfaction, and prediction and improvement of overall outcomes [9]. Further research on effective implementation of thoracic surgery specific PRO instruments is required.

1.3 Purpose and Rationale

Patients undergoing thoracic surgery report maintaining independent physical functioning and quality of life (QOL) are important and influence their treatment decisions [1]. Research has shown readmissions, physical debility, and declines in QOL are common after thoracic surgery but has not identified solutions to improving these problems [2-4]. The rationale of this research is improvement of the patient experience and reduction of readmissions through management of symptoms after thoracic surgery.

A potential approach to managing symptoms after thoracic surgery is using patient-reported outcomes. Assessment of patient-reported symptoms and QOL has improved care in a variety of patient populations. Chemotherapy patients randomized to complete PRO assessments at home with nursing alerts for concerning symptoms had fewer emergency room visits, hospitalizations, and better survival [5, 6]. In lung cancer patients, recurrence was detected earlier using PRO monitoring [7]. Few studies have been done using PROs to improve care in thoracic surgery patients specifically. One trial in this group demonstrated postoperative symptom severity decreased using PROs [8]. This proposal aims to build on prior experience with symptom self-reporting by optimizing a thoracic surgery specific patient-reported symptom survey and rigorously testing its implementation. It is a reasonable expectation this patient population will complete the surveys, as they are highly vested in their post-surgical care. In addition, 2 UNC clinics have integrated PROs successfully, and a multitude of UNC research groups with similar patient populations have successfully piloted PRO studies.

Specific gaps in knowledge on PRO use in thoracic surgery have been identified [9, 10]. Barriers include optimal instruments and timing for PRO collection,

utility of PRO monitoring to providers and patients, and association of changes in PROs with postoperative outcomes. To address these issues, this study will evaluate the implementation of PROs for symptom monitoring in thoracic surgery patients and to assess how PROs correlate to readmissions and declines in global QOL. The overall hypothesis of this study is that PROs can be used to identify opportunities for intervention in patients at risk for poor postoperative recovery.

2.0 STUDY OBJECTIVES AND ENDPOINTS

2.1 Primary Objectives

2.1.1 To determine impact of PRO monitoring with symptom alerts compared to PRO monitoring without symptom alerts after thoracic surgery on post-operative quality of life.

2.1.2 To determine feasibility of 90-day post-operative PRO symptom monitoring after thoracic surgery symptom monitoring eliciting a clinician response.

Feasibility is defined as:

1. $\geq 50\%$ of participants complete all symptom surveys until 3 months post-operatively
2. $\geq 50\%$ of symptom alerts generate a clinician response

2.1.3 To determine barriers/facilitators of PRO monitoring after thoracic surgery through semi-structured interviews of patients and caregivers.

2.2 Secondary Objectives

2.2.1 To determine impact of PRO monitoring with symptom alerts compared to PRO monitoring without symptom alerts after thoracic surgery on post-operative readmission and mortality rates by analyzing:

1. 30-day post-discharge emergency department visit rate
2. 90-day post-discharge emergency department visit rate
3. 30-day post-discharge readmissions rate
4. 90-day post-discharge readmissions rate
5. 30-day mortality (percentage)
6. 365-day mortality (percentage)
7. Change in 2-year quality of life

2.2.2 To determine feasibility of PRO monitoring after thoracic surgery in regards to monitoring long-term quality of life. Feasibility is defined as $\geq 50\%$ of patients completing all quality of life surveys at baseline and all follow-up time points.

3.0 PATIENT ELIGIBILITY

3.1 Inclusion Criteria

Patients participating in PRO monitoring must meet the following inclusion criteria in order to participate in this study:

- 3.1.1 18 years or older
- 3.1.2 English speaking
- 3.1.3 Able and willing to complete web-based symptom survey
- 3.1.4 Be presenting for elective inpatient thoracic surgery

Caregivers willing to participate in semi-structured interview must meet the following inclusion criteria in order to participate in this study:

- 3.1.5 18 years or older
- 3.1.6 English speaking
- 3.1.7 Be a caregiver for a patient who has undergone thoracic surgery and enrolled in the PRO portion of the study

3.2 Exclusion Criteria

All patients meeting any of the following exclusion criteria at baseline will be excluded from study participation:

- 3.2.1 Not completing planned surgery within 3 months of obtaining informed consent
- 3.2.2 Diagnosis of esophageal cancer
- 3.2.3 Inability to read and speak English
- 3.2.4 Presenting for day surgery
- 3.2.5 Presenting for foregut surgery (e.g. paraesophageal hernia repair)
- 3.2.6 Dementia, altered mental status, or any psychiatric condition that would prohibit the understanding or rendering of informed consent.
- 3.2.7 Current incarceration
- 3.2.8 Pregnancy

Caregivers meeting any of the following exclusion criteria at baseline will be excluded from study participation:

[figure not shown]
- 3.2.9 Inability to read and speak English

- 3.2.10 Dementia, altered mental status, or any psychiatric condition that would prohibit the understanding or rendering of informed consent.
- 3.2.11 Current incarceration
- 3.2.12 Not currently providing care for a patient who has undergone thoracic surgery and enrolled in the PRO portion of the study
- 3.2.13 Receiving extensive medical treatment (e.g., caregivers admitted in the intensive care unit)

4.0 STUDY PLAN

4.1 Schema

Figure 1: Study Schema

October 05, 2023

This is a randomized study of 140 participants undergoing thoracic surgery. The primary purpose of this study is to evaluate the implementation of PROs for symptom monitoring in thoracic surgery patients and to assess how management of PROs correlate to readmissions and declines in global QOL. PROs will be administered using the University of North Carolina Patient-Reported Outcomes Core (PRO Core) web-based system. PRO Core maintains a survey system for administering and managing survey reporting. PROs will consist of:

- EORTC QLQ-C30: a cancer-specific survey usable for various cancers
- EORTC QLQ-LC13: a survey used specifically for lung cancer patients
- PROMIS Physical Function SF 4a: a survey used to measure perceived physical mobility and capability
- Pre-operative symptom survey
- Post-operative symptom survey
- Patient Satisfaction survey
- Readmission survey

A subset of 40 patients with varying postoperative experiences and their caregivers will also participate in a semi-structured interview to assess usability and feasibility of the PRO collection.

Patient's active participation is anticipated to last up to approximately 2 years and 3 months. Some patients will have a shortened participation period due to early discontinuation of study procedures.

4.2 Duration of Study

This study will last for approximately 4 years. Up to a total of 140 participants will be enrolled over two years. A subset of approximately 40 patients with varying postoperative experiences and their caregivers will also participate in a semi-structured interview for a total accrual goal of 180 participants. Each patients' participation in the study will last up to 2 years and 3 months. Some patients will have a shortened participation period due to early discontinuation of study procedures. Study analysis of participant data will take place throughout the 4 years.

4.3 Study Details

Participants complete electronic surveys to assess their baseline and post-operative characteristics, symptoms, quality of life, and health outcomes. The study consists of a total number of 9 different surveys.

Figure 2: Survey Frequency and Duration

Survey	Frequency	Completion Time
Pre-operative Symptom Survey	1	5 minutes
Patient Demographics	1	3 minutes
PROMIS Physical Function SF 4a Survey	32	2 minutes
EORTC QLQ-LC13 survey	8	3 minutes
EORTC QLQ-C30 survey	8	8 minutes
Patient Satisfaction survey	7	3 minutes
Readmission Patient Survey	7	2 minutes
Post-operative symptom Daily Survey	15	7 minutes
Post-operative symptom Weekly Survey	11	7 minutes

Enrollment/Baseline Visit

Patients at the multidisciplinary thoracic oncology clinic with plans for thoracic surgery will be approached for enrollment based on inclusion/exclusion criteria described above. An IRB-approved study team member will approach the patient to discuss study procedures, benefits, risks and obtain informed consent prior to any study procedures. The study team member will also teach the patient how to complete the PRO assessment using PRO Core.

At that time, the participant will complete their pre-operative PRO assessment in a private area, which will include PRO surveys as well as demographic questions such as age, sex, and education. PRO survey responses will be reported using the PRO Core database. Paper copies of PRO surveys and source documents will be used if PRO Core system is inaccessible.

For patients who are found to be ineligible during screening or those potentially eligible during screening but found to be ineligible after contact, reasons for ineligibility as well as basic demographics available in the EMR (e.g. race, ethnicity, age, gender, education level if available) will be collected in PRO Core.

For patients who are eligible but refuse enrollment, reasons for refusal, as well as basic demographics available in the EMR (e.g. race, ethnicity, age, gender, education level if available) will also be collected within PRO Core.

Discharge Day (Day 0) Visit:

On the day of discharge (or the next business day in the case of late or weekend discharges), discharge day surveys will be activated in PRO Core by the study staff.

A study team member will call or approach participant in their hospital room before or after discharge to reorient the participant with PRO Core, if needed.

Participants will be reminded of the post-discharge survey schedule, helped with any questions they may have, and assisted with completing any due surveys, if needed.

In the case the day of discharge survey is not obtained (e.g late in the day discharges, weekend discharges, and patient unable or unwilling to complete a survey), this will not be considered a protocol deviation.

The study team member activating the discharge day survey will obtain surgical information from Epic, the surgeon or surgery care team member.

Day 0 (Discharge) to Day 14 Post-Discharge

At this time the following procedures will be performed:

- Daily Post-operative symptom survey
- Daily PROMIS Physical Function SF 4a survey

Day 14 (+/- 7 days) Post-Discharge

At this time the following procedures will be performed:

- EORTC QLQ-LC13 survey
- EORTC QLQ-C30 survey
- Patient Satisfaction survey
- Readmission Patient Survey

Day 15 to Day 90 Post Discharge

Weekly symptom monitoring commences. At this time the following procedures will be performed:

- Weekly Post-operative symptom survey
- Weekly PROMIS Physical Function SF 4a survey

Day 60 Post-Discharge (+60 days)

At this time the following procedures will be performed:

- EORTC QLQ-LC13 survey
- EORTC QLQ-C30 survey
- Patient Satisfaction survey
- Readmission Patient Survey

Day 120 Post-Discharge (+60 days)

At this time the following procedures will be performed:

- EORTC QLQ-LC13 survey
- EORTC QLQ-C30 survey
- PROMIS Physical Function SF 4a survey
- Patient Satisfaction survey
- Readmission Patient Survey

Day 180 Post-Discharge (+185 days)

At this time the following procedures will be performed:

- EORTC QLQ-LC13 survey
- EORTC QLQ-C30 survey
- PROMIS Physical Function SF 4a survey
- Patient Satisfaction survey
- Readmission Patient Survey

Day 365 Post-Discharge (+180 days)

At this time the following procedures will be performed:

- EORTC QLQ-LC13 survey
- EORTC QLQ-C30 survey
- PROMIS Physical Function SF 4a survey
- Patient Satisfaction survey

Day 545 Post-Discharge (+185 days)

At this time the following procedures will be performed:

- EORTC QLQ-LC13 survey
- EORTC QLQ-C30 survey
- PROMIS Physical Function SF 4a survey
- Patient Satisfaction survey

Day 730 Post-Discharge (+185 days)

At this time the following procedures will be performed:

- EORTC QLQ-LC13 survey
- EORTC QLQ-C30 survey
- PROMIS Physical Function SF 4a survey
- Patient Satisfaction survey

Medical chart abstraction will be collected any time after enrollment to capture

clinical events as specified in the protocol.

Semi-Structured Interviews

The PI will identify patients to approach for semi-structured interview. Interviews may also be done with selected participants' caregivers. After the initial participant interviews have been completed, the caregiver interview guide, sampling frame and timeline will be submitted to the IRB once determined. Semi-structured participant interviews will initially be conducted between 14-90 days post-discharge. Sequential interviews will be conducted with the goal to complete 10 interview participants in the 14-90 days post-discharge PRO monitoring phase. Once complete or if there are no more participants in the 14-90 days post-discharge phase, the participants will be chosen purposively to capture patients with varying postoperative experiences and low PRO survey completion rates. Patients who completed the 90-days post-discharge symptom surveys but are in long-term follow-up to 12 months post-discharge may also be interviewed to increase the sample size as the study nears the end of enrollment, as needed. Interviews will be administered using interview guides and will continue until thematic saturation is achieved, which will be defined by no new codes being generated to add to the codebook. Semi-structured interview duration is dependent on individual participant responses, but the duration is expected to be approximately 30-60 minutes. The sample size is anticipated to be approximately 40 interviews with patients. An additional 40 interviews will be conducted with selected participants' caregivers for those participants who agree to have caregivers contacted. The participants who are asked to be interviewed will receive a \$20 gift card for their participation after completion of the interview.

4.4 Expected Risks

Expected risks for this study are likely minimal and involve psychosocial harms such as emotional distress or embarrassment related to PRO questions and breach of confidentiality. PRO questions are similar to questions used in the clinical setting and therefore are unlikely to cause harm. However, should a patient experience emotional distress stemming from these questions, a psychology consult through the Lineberger Comprehensive Cancer Support Program will be obtained. Risk of confidentiality breach will be minimized in several ways.

Study data will be recorded and stored in PRO Core. UNC PRO Core provides a secure platform for the electronic administration of surveys and collection of data from mobile health devices customized to specific research and clinical care applications. PRO Core data are stored in a secure enterprise-level Oracle database hosted by UNC Center for Bioinformatics, and web servers are also hosted by the UNC Center for Bioinformatics.

Data transmitted between the server and end-users are encrypted using SSL, and all databases are encrypted. Only study team members will have access to data stored in PRO Core, and they will use their ONYEN to log in. Research team

members will be instructed to keep all participant data and patient participation confidential.

Approaching patients about enrollment in the clinic poses a risk to privacy. We anticipate this risk to be low. In the UNC Multidisciplinary Thoracic Oncology Clinic, research teams routinely approach patients for enrollment in clinical studies during clinic, either preceding or succeeding their provider visit. To avoid threats of coercion, providers will be educated but not directly involved with recruitment of patients.

Semi-structured interviews will be conducted by CHAI Core research assistant and/or study team member(s) trained in qualitative interviews. Should participants experience emotional distress related to interview questions, a psychology consult through the Lineberger Comprehensive Cancer Support Program will be obtained. Audio files and word documents containing interview materials will be stored on a secure encrypted server. Recorded interviews will avoid using names (and instead assign codes for each participant) to protect confidentiality. Additionally, if names are inadvertently used during interviews, transcripts will be stripped of participant names. A code key which links the participants interview code to their study ID will be housed separately, on a secure server.

4.5 Removal of Patients from Protocol

Patients will be removed from the study if:

- they experience significant emotional distress in response to PRO surveys
- they indicate that they no longer wish to participate

5.0 TIME AND EVENTS TABLE

5.1 Time and Events Table

Study Procedures	Timeline													
	Baseline (90 days)	Discharge (1-7 days)	Days 1-6 (4-10 days)	Day 14 (7-14 days)	Days 14-18 (8-12 days)	Days 21-28 (5-12 days)	Day 60 (4-60 days)	Days 63-70 (7-14 days)	Day 120 (1-60 days)	Day 120 (1-180 days)	Day 165 (4-180 days)	Day 205 (4-180 days)	Day 205 (4-185 days)	Day 205 (4-185 days)
Informed Consent	X													
Eligibility Checklist	X													
Randomization	X													
Participant Demographics	X													
EORTC QLQ30	X		X		X		X	X	X	X	X	X		
EORTC LC18	X			X		X		X	X	X	X	X		
Baseline Symptoms Assessment	X													
Postoperative Symptom Assessment (24h recall)		X	X	X	X									
Postoperative Symptom Assessment (7 day recall)					X		X							
PROMIS Physical Function SF 4a	X	X	X	X	X	X	X	X	X	X	X	X		
Patient Satisfaction Survey				X			X	X	X	X	X	X		
Re-Admission Survey					X		X	X	X					

Note: Semi-structured interviews will begin after 14 days of discharge

6.0 UNANTICIPATED PROBLEMS

6.1 Definition

As defined by UNC's IRB, unanticipated problems involving risks to study subjects or others (UPIRSO) refers to any incident, experience, or outcome that:

- Is unexpected (in terms of nature, severity, or frequency) given (a) the research procedures that are described in the protocol-related documents, such as the IRB-approved research protocol and informed consent document; and (b) the characteristics of the subject population being studied;
- Is related or possibly related to a subject's participation in the research; and
- Suggests that the research places subjects or others at a greater risk of harm (including physical, psychological, economic, or social harm) related to the research than was previously known or recognized.

6.2 Reporting

Any UPIRSO that occurs during the conduct of this study and that meets all three criteria listed in 6.1 must be reported to the UNC IRB using the IRB's web-based reporting system.

7.0 STATISTICAL CONSIDERATIONS

7.1 Study Design

This is a single center, randomized feasibility study. A total of 140 patients undergoing thoracic surgery will be prospectively enrolled and randomized in a 1:1 ratio. A random block method with blocks of 20 will be utilized to randomize participants to one of two arms to complete PRO (patient reported outcome) symptom monitoring. The two arms are 1) active symptom monitoring and 2) passive symptom monitoring. The participants randomized to active symptom monitoring will have alerts sent to their clinicians when their PRO symptom scores exceed baselines scores by 2 points or more, or when 'severe' or 'very severe' symptoms are reported. Participants randomized to the passive PRO monitoring arm will complete the same PROs as participants in the active monitoring arm, but will not have alerts sent to their clinician. All participants will be administered survey instruments to further assess quality of life including: EORTC QLQ30, EORTC LC13, PROMIS Physical Function SF 4a survey SF 4a. Additionally, in order to assess the feasibility of the PRO monitoring system, all participants will be asked to complete a Patient Satisfaction survey. In addition, a subset of 40 participants and 40 caregivers will be chosen to complete a semi-structured interview, if willing, to assess patient satisfaction with symptom monitoring experience. The subset will be made up of a range of post-operative experiences and will be a fair representation of study population, including both

study arms. Participants will be chosen by principal investigator and eligible to participate in interview after 14 days of discharge

The primary objectives are to determine 1) impact of PRO monitoring with symptom alerts compared to PRO monitoring without symptom alerts after thoracic surgery on post-operative quality of life 2) feasibility of 3-month post-operative PRO symptom monitoring after thoracic surgery symptom monitoring eliciting a clinician response 3) barriers/facilitators of PRO monitoring after thoracic surgery through semi-structured interviews of patients.

Secondary objectives include: 1) determining impact of PRO monitoring with symptom alerts compared to PRO monitoring without symptom alerts after thoracic surgery on post-operative readmission and mortality rates 2) determining feasibility of PRO monitoring after thoracic surgery in regards to monitoring quality of life.

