7.2 Sample Size and Accrual

We originally anticipated 100-150 patients to be enrolled per year. A sample size of 66 in each group will have 80% power to detect a difference in mean EORTC scores of 10.000 assuming that the common standard deviation is 22.900 using two group t-test with a 0.050 one-sided significance level. The target sample size was 140 patients to allow appropriate block randomization in groups of 20. Based on enrolling about 140 patients, we would be powered to detect an effect size of 0.437 (difference in means of 10, common standard deviation of 22.9). Due to slower accrual in context of COVID-19, we anticipate enrollment of 100-140 patients before funding ends. With 100 patients, we will have 80% power to detect an effect size of 0.501 (difference in means of 11.467, common standard deviation of 22.9). Power calculations were performed using SAS version 9.4 (SAS Inc., Cary, NC) using PROC POWER and a two sample means difference test.

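### Section 7.1 prints a single fixed block size of 20 and no concealment of past allocations is described; hidden, varying block sizes would be a cheap improvement

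*Combined protocol and SAP*

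**What the plan says.** Section 7.1 describes the allocation: "This is a single center, randomized feasibility study", with patients "randomized in a 1:1 ratio". It adds: "A random block method with blocks of 20 will be utilized to randomize participants to one of two arms". No second block size, variation in size or stratification factor is given. Section 7.2 confirms that the size is fixed: "The target sample size was 140 patients to allow appropriate block randomization in groups of 20". The same section now expects fewer patients: "we anticipate enrollment of 100-140 patients before funding ends".

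On recruitment, section 4.3 states: "An IRB-approved study team member will approach the patient to discuss study procedures". One inclusion criterion in section 3.1 calls for judgement: "Able and willing to complete web-based symptom survey". Section 4.4 keeps treating providers from direct involvement in recruitment, as a guard against coercion.

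Masking is not stated. Both arms complete the same surveys. Clinicians receive alerts for the active arm, while passive-arm patients complete the surveys "but will not have alerts sent to their clinician". No section says who holds the allocation list, how an allocation is released, or who can see earlier ones. The table in section 5.1 puts consent, eligibility, randomization and baseline quality of life in one baseline column without an order. Section 4.3 does place consent ahead of all study procedures.

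**The concern.** In a 1:1 block of 20, once one arm has received 10 patients, every remaining allocation in the block must go to the other arm. A person who knows the block size, where the block began and every allocation so far can see this coming. Concealing the future list does not prevent it, because the information lies in past allocations.

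If that person also recruits, there is room to act. The study team decides whom to approach and judges who can and will complete web surveys. The first primary objective (section 2.1.1) compares self-reported quality of life between arms. Enrolling patients with a better or worse outlook when the next arm is known would shift that comparison. The t and Wilcoxon tests at each time point (section 7.3.1) make no adjustment that would remove the shift.

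**Working it through.** **Inputs.** From sections 7.1 and 7.2: block size b = 20; ratio 1:1, so m = 10 per arm per block; one centre, no strata; 100 to 140 patients, or 5 to 7 blocks. From section 7.2: planned difference 10, SD 22.9, one-sided 0.05, 66 per group. Assumed, because the documents give no figure: patients steered toward one arm differ from those steered toward the other by 10 points, with 20 points as a wider case.

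**The plan's own figures.** The plan gives no predictability figure. Its target is consistent with the block size: 140/20 = 7 full blocks. Its sample size reproduces: the exact t-test calculation gives 80.25% power at 66 per group and 79.7% at 65.

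**Allocations known with certainty.** The expected number per block is b/(m + 1) = 20/11 = 1.82, and 1.82/20 = 9.1%. A simulation of 200,000 blocks also gave 9.1%. Over the trial this is 7 × 1.82 = 12.7 of 140 patients, or 5 × 1.82 = 9.1 of 100. The last allocation in a block is always certain. The one before it is also certain with probability 9/19 = 47%, so in the other 53% of blocks only the last is certain.

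**Best guess at every step.** Always guessing the arm used less so far gives m + 2^(b−1)/C(b, m) − 1/2 correct per block:

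10 + 524,288/184,756 − 0.5 = 12.34 of 20 = 61.7%, against 50% by chance.

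**Other fixed sizes.** The certain share is 1/(m + 1):

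| Known fixed block size | Certain allocations |
|---|---|
| 4 | 33.3% |
| 6 | 25.0% |
| 8 | 20.0% |
| 10 | 16.7% |
| 20 | 9.1% |

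**Possible bias in an unadjusted comparison.**
- Only certain allocations acted on: 0.091 × 10 = 0.9 points, or 0.9/22.9 = 0.04 SD.
- Every guess acted on: (2 × 12.34/20 − 1) × 10 = 0.234 × 10 = 2.3 points.
- With the wider 20-point assumption these become 1.8 and 4.7 points.

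All are upper limits, set against a planned difference of 10. They require every such opportunity to be used, always in the same direction.

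**Hidden varying sizes.** Blocks of 12, 16, 20 and 24 chosen at random (average 18) were simulated at 140 patients. Even a recruiter who tracks every allocation and knows the set of possible sizes would be certain of only about 0.6%. The best-guess rate stays at 61.8%. The share removed is 9.1% − 0.6% = 8.5%, worth 0.085 × 10 = 0.85 points under the 10-point assumption. The final difference in arm sizes averages 1.2 patients, with a maximum of 8. Even at 8 (74 against 66), the effective size per arm is 2 × 74 × 66/140 = 69.8 instead of 70.

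**The case against.** The case against is substantial, and most of it stands.

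- **The 9.1% is conditional.** A reader might infer that 9% of allocations are in fact known in advance. The documents do not support that. It holds only for someone who sees every earlier allocation in the block, and nothing says recruiters do.
- **Masking is not stated.** A reader might infer that the trial is unmasked throughout. Some staff must know the arm: section 7.1 has the principal investigator choosing interviewees from both arms. That does not show that recruiters know it. Running the surveys reveals nothing, since they are the same in both arms. Alerts begin only after discharge, with surgery up to 3 months after consent, and need a symptom to trigger them, so they give a poor running count of the open block.
- **Safeguards exist.** Under section 4.4 treating providers, who would receive alerts, are not directly involved in recruitment. This does not cover study team members, who do recruit. Section 4.3 records reasons for ineligibility and refusal, which leaves a partial audit trail, though not clearly for patients never approached.
- **The mixed model helps.** The section 7.3.1 model analyses change over time with a random intercept, so a stable baseline difference would be partly absorbed. It names no other covariates, and the tests at each time point stay unadjusted.
- **Twenty is a large block.** A reader might infer that a smaller fixed block would be safer. The table above shows the opposite.
- **The remedy is partial.** Varying sizes do not lower the best-guess rate, so the 2.3-point scenario remains. Section 7.2 describes accrual that has already slowed, so some blocks may be finished. No count of randomized patients is given, so the text cannot show that the change would come too late.

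**Conclusion.** The point holds as a minor design improvement. The plan discloses one fixed block size in an unstratified single-centre sequence and describes neither masking of study staff nor concealment of past allocations. For a recruiter who can see all earlier allocations, 9.1% would be certain. Hidden varying sizes bring that below 1%, while guessing stays right about 62% of the time. The gain is therefore at most about 0.9 quality-of-life points under the assumed 10-point steering effect, and only in the unadjusted tests. It is smaller if blocks are already complete.

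A reader might go further and infer that enrolment has been selective or that the primary comparison is biased. The documents give no evidence of either. Selective enrolment remains a possibility that the plan could close off cheaply.

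**What to change.** For blocks not yet opened:

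1. Replace the fixed size in section 7.1 with randomly varying block sizes averaging about 20. State in the protocol only that sizes vary.
2. Keep the sizes and the list in a document that recruiting staff do not see.
3. Release each allocation only after consent, eligibility and baseline quality of life are recorded, and say so in sections 4.3 and 5.1. Consent first is already required; the order of the other two is not stated.

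A smaller fixed block should not be substituted. The cost is a new list for the remaining blocks, a short amendment, matching wording in section 7.2, and a final arm imbalance of about one patient on average (single digits at most), with negligible loss of power.
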